### 6.2.3 Adjustments for Covariates

No statistical analysis assessment of possible covariate effects is planned.

### 6.2.4 Multiple Comparisons/Multiplicity

No adjustments for multiplicity will be made.

### 6.2.5 Subgroups

Subgroups analyses are not planned.

### 6.2.6 Missing, Unused, and Spurious Data

Data will be analyzed as observed. No imputation for missing data will be performed unless otherwise specified.

For binary endpoints participants who discontinue treatment will be considered as non-responders.

No other imputation of missing endpoints will be used.

For partial or missing AE start dates the following imputation will be applied:

1. If year is not missing and is after the year of first dose:
  - a. If month is missing, then month will be imputed as January.
  - b. If day is missing, then day will be imputed as the first of the month.
2. If year is not missing and is the same as the year of the first dose:
  - a. If month is missing, then impute the month as the month of the first dose date.
  - b. If day is missing, and the month is the same as the month of the first dose date, then impute day as the day of the first dose date.
  - c. If day is missing but month is after the month of first dose date, then impute day as the first day of the month.
3. If year is missing then impute the year as the year of the first dose date:
  - a. If month is missing, then impute the month as the month of the first dose date.
  - b. If day is missing, then impute the day as the day of the first dose date.
4. If the start date is completely missing, but the AE is either ongoing or the stop date is after the first dose date then impute the start date as the first dose date.
5. For any cases involving the rules above, if the AE end date is before the AE start date, then do not impute the AE start date and assume that the AE is treatment emergent for the

purpose of the analysis. Further, if the AE stop date occurs prior to the first dose date, do not impute the AE start date, and assume that the AE is not treatment emergent.

No imputations will be applied to AE stop dates.

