### 6.6.1 Adverse Events

Adverse events will be coded using MedDRA and will be graded using the severity scale specified in the protocol. .

Summaries of AEs will be based on treatment emergent AEs (TEAEs), defined as AEs with an onset at the time of or following the start of treatment, or medical conditions present before the start of treatment that increase in severity or relationship at the time of or following the start of treatment.

Adverse events are summarized by participant, therefore, in any tabulation, a participant contributes only once to the count for a given adverse event (SOC or PT).

Separate tabulations may also be produced for TEAEs assessed as related to study drug (related, probable, or possible relationship), TEAEs that led to discontinuation from study, TEAEs that led to death, TEAEs greater than or equal to Grade 3 in severity and TEAEs by highest grade. Common AEs will be summarized by MedDRA PT from most to least common. Treatment emergent SAEs and treatment emergent SAEs related to study drug will also be tabulated.

No formal hypothesis-testing analysis of adverse events incidence rates will be performed.

All adverse events occurring on study will be listed in subject data listings.

By-subject listings also will be provided for the following: participant deaths; serious adverse events; and adverse events leading to study discontinuation.

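### When an AE start date lacks the year but has the month, SAP 6.2.6 rule 3 can put the event on the wrong side of first dose, in either direction

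*SAP*

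**What the plan says.** AE incidence is a primary endpoint (SAP 3.1). SAP 6.6.1 states: "Summaries of AEs will be based on treatment emergent AEs". An AE qualifies if it begins at or after first dose. Conditions already present that worsen in severity or relationship also count. The same section lists all on-study AEs.

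SAP 6.2.6 gives five rules for incomplete AE start dates:

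- Rules 1 and 2 apply when the year is known. Rule 2 compares a known month with the first-dose month before it imputes the day.
- Rule 3: "If year is missing then impute the year as the year of the first dose date". Its sub-rules read "If month is missing, then impute the month as the month of the first dose date" and "If day is missing, then impute the day as the day of the first dose date". A recorded month is therefore kept, and it is not compared with the first-dose month.
- Rule 4: "If the start date is completely missing, but the AE is either ongoing or the stop date is after the first dose date", the start becomes the first-dose date.
- Rule 5, first part: "if the AE end date is before the AE start date, then do not impute the AE start date", and the AE is assumed treatment emergent. Second part: "if the AE stop date occurs prior to the first dose date, do not impute the AE start date", and the AE is assumed not treatment emergent.

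AEs are collected from consent to the final visit (schedule footnotes, SAP 9.1). The run-in covers about Day -56 to -1 (SAP 5.2) and can be extended. The last scheduled visit before extended follow-up is Day 168, 251 or 195 in Cohorts 1, 2 and 3 (SAP 2.1). The length of the extended follow-up is redacted.

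**The concern.** The first-dose year is a sensible default only if a participant's whole study time lies in one calendar year. With at least 56 days before dosing and 168 to 251 days after it, many participants will cross a year end. For them a recorded month can contradict the imputed year, and rule 3 never checks. The imputed start decides whether the AE counts as treatment emergent, and the TEAE tables carry a primary endpoint in cohorts of 4 to 12.

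The rules also treat better information less cautiously. Take a post-dose AE that is still ongoing. If nothing is known of its start, it is dated to first dose and counted. If its month is known to be in the next year, it is dated before treatment and not counted.

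**Working it through.** The plan states no figure to reproduce. The check applies rule 3 as written and then asks whether rules 4 or 5 catch the result.

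**Two examples (dates assumed)**

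| | A: post-dose AE | B: run-in AE |
|---|---|---|
| First dose | 16 Oct 2023 | 15 Jan 2024 |
| True onset | 10 Feb 2024 (Day 118) | 10 Dec 2023 |
| Recorded start | 10 Feb, no year | 10 Dec, no year |
| Rule 3 start | 10 Feb 2023 (16 Feb 2023 if the day is also missing) | 10 Dec 2024 |
| Side of first dose | before (wrong) | after (wrong) |

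- *A, rule 4:* needs a completely missing start, so it does not apply.
- *A, rule 5:* an end date cannot precede a start that has been moved a year too early, and the AE did not stop before first dose. Neither part acts. The imputed start is 248 days before dosing, against a run-in of about 56 days.
- *B, ongoing:* no rule acts and the AE is counted as a TEAE.
- *B, stopped after first dose but before 10 Dec 2024:* the first part of rule 5 acts and also makes it a TEAE.
- *B, stopped before first dose:* both parts of rule 5 are met and point opposite ways. Only if the second part governs is the result correct.

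**How general is A?** Rule 3 was applied to every first-dose date in a 365-day year and every onset from Day 1 to the last scheduled visit, Day T. An onset on Day s falls in the next calendar year for s - 1 of the 365 first-dose dates. The number of next-year pairs is therefore T(T - 1)/2 out of 365T, a share of (T - 1)/730.

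| Cohort | T | Next-year pairs | Share of days | Dated before first dose |
|---|---|---|---|---|
| 1 | 168 | 168 × 167/2 = 14,028 | 167/730 = 23% | 14,028 (100%) |
| 2 | 251 | 251 × 250/2 = 31,375 | 250/730 = 34% | 31,375 (100%) |
| 3 | 195 | 195 × 194/2 = 18,915 | 194/730 = 27% | 18,915 (100%) |

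The 100% holds whether or not the day is known. Onsets in the first-dose year are never misdated this way. If month and day are missing too, the start becomes the first-dose date and the error is 0%.

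**How general is B?** Under the same even spread, run-in Day -k falls in the previous calendar year for k of 365 first-dose dates. Averaged over k = 1 to 56, that is 57/730 = 8% of run-in days. By days at risk, A is the commoner case, but B is not excluded.

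**Beyond the last scheduled visit.** Because the length is redacted, a range was run. Of onsets in a later calendar year, the share dated before first dose is 100% with follow-up to Day 365 (92% if the day is missing), 85% (78%) to Day 400 and 63% (59%) to Day 540. It falls because an onset a year or more after dosing can land on or after first dose.

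**Effect on a table row.** One participant is 1/4 = 25, 1/6 = 17 or 1/12 = 8 percentage points. SAP 6.6.1 counts each participant once per system organ class or preferred term, so the row changes only if the misdated AE is that participant's sole event in it.

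**The case against.** The strongest reply is that the rule will hardly ever be used. AEs are asked about at visits and weekly contacts up to the last scheduled visit, the investigator reports onset date and time (Protocol 8.5), automated checks look for missing data (Protocol 10.5), and missing data must be explained (Protocol 11). The contact date will normally settle the year. This stands, and it is why the point is minor. It is weaker in extended follow-up, which has four remote contacts and one site visit (Protocol 7.15). The rule is also written for exactly the dates that escape these checks.

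It is also fair that the listings keep every AE, that the worsening clause can bring some events back, and that rule 3 gives a cautious answer when the whole date is missing. The fault is one sub-case, not a reversal of the section's approach.

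A reader might infer that the error always removes post-dose events and so flatters the safety profile. The documents do not support that. AEs are recorded from consent, so example B can occur and adds a false TEAE. A reader might also infer that each lost event costs 17 to 25 points. That needs a cohort of 4 to 6 and a participant with no other event in the row.

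**Conclusion.** The point holds as a minor error in a stated rule. When the year is missing and the month is known, rule 3 misdates every next-calendar-year onset up to Day 168, 251 or 195 to before first dose. It can also move a run-in AE from the previous calendar year to after first dose. Rules 4 and 5 do not reliably correct either case.

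The 23%, 34% and 27% assume evenly spread first-dose and onset dates. They are shares of days on study, not of AEs expected to be misclassified. The documents give no frequency for such dates. Neither the number of affected events nor the net direction can be derived, and nothing here shows that any reported incidence is wrong.

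**What to change.** Amend rule 3 for a missing year with a known month:

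1. Choose the year that places the start between informed consent and the earlier of the AE stop date and the participant's last assessment date (or data cut-off). If the day is missing, judge the fit by month.
2. If more than one year or no year fits, or if it stays unclear whether the start is before or after first dose, do not impute the date. Treat the AE as treatment emergent unless the stop date is before first dose.

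Step 2 follows the default already in rules 4 and 5. The upper limit should be the participant's own last assessment, not only the data cut-off. Otherwise an ongoing run-in AE could be moved past that participant's follow-up.

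Both examples then resolve. With a 56-day run-in, consent is about 21 Aug 2023 in A, so only February 2024 fits. In B it is about 20 Nov 2023, and 10 Dec 2024 would be Day 331, beyond all three last scheduled visits, so December 2023 fits. More generally, a 56-day run-in plus scheduled follow-up spans 224, 307 and 251 days (56 + 168, 56 + 251, 56 + 195). All are under a year, so two years can fit only with a longer run-in or extended follow-up.

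The cost is a sentence or two in the SAP and a few lines of code. The downside is that a few run-in AEs with ambiguous dates may be counted as TEAEs.

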## 6.3 Study Population

### 6.3.1 Subject Disposition

Subject disposition will be presented, including the number screened, the number dosed, and the number that have completed, discontinued, or are ongoing in the study and reasons for discontinuation. The number of participants in each analysis set will also be presented.

The summaries will be presented by cohort and overall. The denominator for all percentages will be the total number of participants in each cohort.

The following by-subject listings will be presented.

- Study completion information, including the reason for premature study withdrawal.
- Inclusion/exclusion criteria
- Inclusion in study Analysis Sets; Reasons for exclusion from the Efficacy, PK, or PD analysis sets
- Protocol deviations

### 6.3.2 Demographic and Baseline Characteristics

Baseline, demographic and medical history information will be summarized for the Safety and Efficacy analysis sets using descriptive statistics.

Medical history will be coded using MedDRA and summarized by System Organ Class (SOC) and Preferred Term (PT). No formal statistical comparisons will be performed.

Baseline disease characteristics will include the type of HAE (Type 1 or 2), Age of onset of first angioedema symptoms (Years), and the Number of hereditary angioedema attacks in the previous 12 months.

Demographic and Baseline data will be provided in data listings.

### 6.3.3 STAR-0215 Administration

STAR-0215 Administration details will be listed by cohort.

## 6.4 Efficacy Evaluation

All analyses of HAE attack data will be presented using the Efficacy Analysis Set. Both Run-In and Post-Treatment period will be displayed where applicable.

All HAE attacks that occurred on study will be listed for both Run-In and Treatment periods.

A summary of Run-In period HAE attack assessments will include Location of HAE attacks (Abdominal, Laryngeal, Peripheral); the baseline (Run-In period) values of: HAE attack rate, HAE attacks by worst severity (none/attack-free, mild, moderate, and severe), duration of each participants longest HAE attack, number and proportion of HAE attacks requiring on-demand therapy, and HAE Attack Free Days. This summary will be repeated for the first dose period.

### 6.4.1 Change from Baseline in Monthly HAE attack rate

HAE attack rate will be expressed as the number of unique investigator-confirmed HAE attacks per month. Only unique (non-overlapping) HAE attacks will be counted; attacks are considered overlapping when a start date falls within 24 hours of an earlier attack's end date. The HAE attack rate will be calculated as:

$(\text{number of HAE attacks} / \text{duration of evaluation period in days}) * 30.4375$ ; where the duration of participants' run-in period and post-treatment follow-up periods is defined in [Section 9.1](#) and [section 5.2 \(Treatment period\)](#).

Change from baseline (Run-In period) to on treatment HAE attack rate, will be summarized by the absolute and percentage change from Baseline. Descriptive statistics (mean, median, standard deviation, Q1, Q3, minimum and maximum values) and 95% CI will be presented. The proportion of participants with a clinical response to treatment will be presented in increments as greater than or equal to 50%, 70%, and 90% reduction of HAE attacks.

A plot of individual participant's HAE attacks over time will display duration and severity by cohort. The plot will begin in the run-in phase through the last HAE assessment. The scheduled dose(s) of each cohort will be represented with dotted-lines. This plot will also be created by HAE attack location or overall cohort plot (combining participants).

HAE attacks per month (attack rate) will be presented at 4-week intervals (28 Days) from treatment start; first dose period, and 3 and 6 month intervals following last dose; and the first 3 and 6 months from Baseline (from initial dose) will also be provided. The mean monthly rate, change from baseline, and 95% CI will be presented; percent change will also be presented for monthly rates. Additional analysis of participants who have completed each interval may be performed.

Analysis of overall HAE attack rate or certain intervals, will be performed on sub-categories of HAEs: by HAE severities Mild, Moderate, Severe, and Moderate or Severe; and those that required therapy (“rescue medication”).

#### 6.4.2 HAE Attack Incidence and Severity

The incidence and proportion of HAE attacks by worst severity (none/attack-free, mild, moderate, and severe) will be summarized.

The proportion of participants who are attack free for the entire treatment period; first dose period, and in 3 month intervals following second/last dose; and the first 3 months and 6 months from Baseline will be summarized.

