4.5. Duration of Treatment and Duration of Study

Individual participants will receive 1 dose of STAR-0215 (Cohort 1; Day 1) or 2 doses (Cohort 2; Days 1 and 84, and Cohort 3; Days 1 and 28). The duration of study participation for each participant, including the Screening and Run-In period, is up to [REDACTED], or [REDACTED] days in Cohorts 1, 2, and 3, respectively. The study is composed of 3 periods, as follows:

- Screening/Run-In: at least 56 days
- Treatment Period: Individual participants will receive STAR-0215 on Day 1 (Cohort 1), Day 1 and 84 (Cohort 2), or Day 1 and 28 (Cohort 3).
- Follow-up Period: approximately 6 months after the last dose of STAR-0215 (Day 168 for Cohort 1, Day 251 for Cohort 2, and Day 195 for Cohort 3). At this time, participants who are willing and eligible to consent can begin participation in the long-term open label extension study (STAR-0215-202).
- Follow-up Period: For participants who do not participate in the long-term open label extension study, monitoring will be performed through [REDACTED] months after the last dose of STAR-0215 in all cohorts (Day [REDACTED] in Cohort 1, Day [REDACTED] in Cohort 2, and Day [REDACTED] in Cohort 3) through regular contacts and scheduled study visit.

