8. Agree not to donate or store eggs or undergo assisted reproductive or fertility treatment during the study and for a total of ■ months after the last dose of STAR-0215.

9. Experienced at least 2 HAE attacks during the Run-In period, as confirmed by an investigator based on meeting the protocol-specified definition of an HAE attack ([Section 7.12](#)).

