9.6. Efficacy Analysis

Unless otherwise specified, all analyses of HAE attack data will be presented similarly during the Run-In and treatment periods using the Efficacy Analysis Set. Data will be summarized for all investigator-confirmed HAE attacks.

The frequency and duration of HAE attacks will be presented with descriptive statistics overall and by participant. The following categories will be presented for attack duration: shorter than 12 hours, 12 to 24 hours, 24 to 48 hours, and longer than 48 hours.

Attack severity categorized as Mild, Moderate, or Severe will be presented overall and by participant.

The number and type of on-demand therapies used to treat HAE attacks will be summarized.

The proportion of HAE attack-free participants during the treatment period will be summarized.

The time normalized number of investigator-confirmed HAE attacks per month (attack rate) will be presented at 4-week intervals and at the end of the study. The mean monthly rate and 95% confidence interval will be presented.

To assess HAE attacks within a participant, the actual and percentage change from baseline (Run-In period) in monthly attack rate with respect to on-treatment attack rate will be calculated. The mean change and 95% confidence interval will be presented.

The proportion of participants with a clinical response to treatment will be presented in increments as greater than or equal to 40%, 50%, 60%, 70%, 80%, 90%, and 100% reduction of HAE attacks relative to baseline will be presented.

Time to first HAE attack after first and last dose of STAR-0215 will be presented using Kaplan-Meier estimates.

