## 2 STUDY DESIGN

### 2.1 Introduction

STAR-0215-201 is a multicenter, single- and multiple-dose study to assess the safety, tolerability, clinical activity, PK, PD, and immunogenicity of STAR-0215 in participants with Type I or Type II HAE. STAR-0215 is a humanized IgG1 kappa light mAb, designed to be a highly potent and specific inhibitor of plasma kallikrein, with a YTE-modified Fc domain to enable delayed clearance and prolonged time in circulation. The study design is a standard approach to the evaluation of the safety and tolerability of an investigational product.

Properly consented participants will undergo screening assessments according to the inclusion and exclusion criteria (Protocol Section 5.1 and Section 5.2, respectively) and immediately enter the Run-In period. During the Run-In period, HAE attack information will be collected to determine if a participant meets the eligibility requirement of experiencing at least 2 HAE attacks during this time period and to establish a baseline prior to STAR-0215 administration. If a participant has an HAE attack during the Run-In period before Day 1 (first dose of STAR-0215), all signs and symptoms of the HAE attack must be resolved before dosing. A washout period for on-demand treatment is not required. The Run-In period may be extended after consultation with the Medical Monitor. In Cohorts 2 and 3, if a participant has an HAE attack immediately before the second dose (Day 84 and Day 28, respectively), signs and symptoms of the HAE attack should be improving per participant report prior to STAR-0215 administration; a washout period for on-demand treatment is not required before the second dose is administered.

In Cohort 1, each participant who has completed the Run-In period and is eligible for STAR-0215 administration will receive 1 dose of STAR-0215 on Day 1. When Cohort 1 has completed dosing, the [Safety Review Committee \(SRC\)](#) will review the cohort's cumulative safety data from the Screening/Run-In period through 21 days after dosing. Progression to Cohort 2 dosing will occur if there are no concerning safety signals. (Protocol Section 4.2)

In Cohort 2, each eligible participant will receive 2 doses of STAR-0215, the first on Day 1 and the second on Day 84. [REDACTED]

In Cohort 3, each eligible participant will receive 2 doses of STAR-0215, the first on Day 1 and the second on Day 28.

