#### 3.2 Secondary Endpoints - Efficacy

- Change from baseline in monthly HAE attack rate, overall and per month.
  - 50%, 70%, and 90% overall reduction of HAE attacks
  - Investigator assessed HAE Attack definition is given in Protocol section 7.12.1:

To be considered an HAE attack, the Investigator must confirm that the event has signs or symptoms consistent with an HAE attack that meet at least 1 of the following criteria: Peripheral angioedema, Abdominal angioedema, or Laryngeal angioedema.

Prodromal symptoms or participant-reported use of on-demand HAE attack treatment alone are not sufficient to define an event as an HAE attack.

Each HAE attack must be unique. To be distinct from the previous attack, the new symptoms must occur at least 24 hours after resolution of the prior attack's symptoms.

The HAE attack resolution is defined as the participant no longer having symptoms of the HAE attack. The HAE attack severity will be graded by the Investigator.
- Proportion of participants who are HAE attack free
- Incidence of at least one HAE attack by maximum severity (mild, moderate, and severe), including participants without any attacks.
- Duration of HAE attack (shorter than 12 hours, 12 to 24 hours, 24 to 48 hours, and longer than 48 hours).
- The number of HAE attacks requiring on-demand therapy.
- Time to first HAE attack after first and last dosing, censored to End of Study visit.
- HAE attack free days, from treatment start until End of Study.

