#### 6.2.2 Definition of Baseline

For the analysis of HAE attacks, the Run-In Period will be considered as Baseline for rate, incidence or duration of HAE attacks.

For all other endpoints baseline is defined as the last non-missing assessment prior to the first dose of STAR-0215.

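### The attack-severity summary takes each participant's worst attack over windows of unequal length, so it tends to move with days observed as well as with the drug

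*SAP*

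**What the plan says.** SAP 3.2 words the secondary severity endpoint as "Incidence of at least one HAE attack by maximum severity (mild, moderate, and severe), including participants without any attacks". SAP 6.4.2 analyses it so: "The incidence and proportion of HAE attacks by worst severity (none/attack-free, mild, moderate, and severe) will be summarized". The category for attack-free participants, and their inclusion in 3.2, show that each participant contributes one value.

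The windows come from other sections:

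- **Run-in.** SAP 6.2.2 states that "the Run-In Period will be considered as Baseline for rate, incidence or duration of HAE attacks". Protocol 4.5 gives "Screening/Run-In: at least 56 days", and SAP 2.1 adds "The Run-In period may be extended after consultation with the Medical Monitor". Inclusion criterion 9 requires "Experienced at least 2 HAE attacks during the Run-In period, as confirmed by an investigator".
- **First-dose period.** SAP 6.4 lists worst severity in the run-in summary and adds "This summary will be repeated for the first dose period". SAP 5.2 ends this period at the second dose, Day 84 in Cohort 2 and Day 28 in Cohort 3.
- **Treatment period.** SAP 5.2 ends it at Day 168, 251 or 195 in Cohorts 1, 2 and 3. SAP 6.4.2 names no window for worst severity. That the full period is tabulated follows from the general statement in SAP 6.4 that run-in and post-treatment are both displayed where applicable.

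Protocol 9.6 says of severity only: "Attack severity categorized as Mild, Moderate, or Severe will be presented overall and by participant". SAP 6.4.1 separately plans monthly attack rates for mild, moderate, severe, and moderate-or-severe attacks.

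**The concern.** A participant's worst attack is the maximum of however many attacks were recorded. With more days there are more attacks, and the maximum can only stay or rise. Run-in is longer than Cohort 3's first-dose period and much shorter than any cohort's treatment period, so comparing the columns mixes a change in severity with a change in exposure. The attack-free category adds a second distortion: the entry rule holds it at 0% in run-in, so any attack-free participant after dosing looks like a gain.

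At stake is the reading of a named secondary endpoint, and of the interim efficacy results that may inform adding participants to Cohorts 2 or 3. The table can point the wrong way when the drug has no effect or a modest one. Between cohorts it mixes regimen with window length.

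**Working it through.** The documents give no sample size calculation and no expected severity figure, so there is no stated number to reproduce. The check asks what the table would show if the drug did nothing.

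**Inputs from the documents.** Run-in 56 days with at least 2 attacks; first-dose period 28 − 1 = 27 days (Cohort 3) and 84 − 1 = 83 days (Cohort 2); treatment period 168, 251 and 195 days (Cohorts 1, 2, 3); 30.4375 days per month (SAP 5.2).

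**Assumptions, not in the documents.** Poisson attacks at a constant rate r per month; each attack severe with probability s, the same before and after dosing. Central case r = 2, s = 20%; ranges r = 1 to 3 and s = 10% to 30%.

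**Formulas.** After dosing, over T days: P(worst = severe) = 1 − exp(−r·s·T/30.4375) and P(none) = exp(−r·T/30.4375). In run-in, with m = r·56/30.4375 and at least 2 attacks required:

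P(worst = severe) = 1 − e^(−m)·[e^(m(1−s)) − 1 − m(1−s)] / [1 − e^(−m)(1+m)].

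**Run-in, central case.** m = 2 × 56/30.4375 = 3.680. Numerator: 0.02523 × (18.987 − 1 − 2.944) = 0.3796. Denominator: 1 − 0.02523 × 4.680 = 0.8819. Result: 1 − 0.3796/0.8819 = 57.0%.

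**Share with worst severity severe, s = 20%**

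| Window | No effect, 1/month | No effect, 2/month | 50% fall from 2/month | 90% fall from 2/month |
|---|---|---|---|---|
| Run-in, 56 days | 45% | 57% | 57% | 57% |
| Cohort 3 first dose, 27 days | 16% | 30% | 16% | 4% |
| Cohort 2 first dose, 83 days | 42% | 66% | 42% | 10% |
| Cohort 1 treatment, 168 days | 67% | 89% | 67% | 20% |
| Cohort 3 treatment, 195 days | 72% | 92% | 72% | 23% |
| Cohort 2 treatment, 251 days | 81% | 96% | 81% | 28% |

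A 70% fall from 2 per month gives 48%, 54% and 63% over 168, 195 and 251 days, close to the 57% in run-in.

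**Two causes in the Cohort 3 first-dose column.** Without the entry rule, run-in would give 1 − exp(−2 × 0.2 × 56/30.4375) = 52%, so window length alone takes 52% to 30% and the entry rule adds about 5 points. Attack-free participants go from 0% by design to exp(−2 × 27/30.4375) = 17% with no drug effect.

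**Chance in a cohort of 6** (simulation, 40,000 cohorts, 2 per month, no effect). Cohort 2 shows more severe participants over treatment than in run-in in 93% of cohorts. Cohort 3's first-dose period shows fewer in about 75%. With a true 50% fall, Cohort 2 still shows more in 73%.

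**Sensitivity.** For s = 10% to 30% and 1 to 3 attacks per month, the no-effect directions for Cohort 3's first dose and for full treatment do not change. They also hold with an 84-day run-in (68% in run-in against 89% to 96% over treatment) and with rates varying between participants (mean 2 per month, CV 0.8: 61% against 86% to 92%). Apparent worsening over treatment reverses only below about 0.3 to 0.5 attacks per month; at 0.5 per month, 24% would have 2 attacks in 56 days.

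**The alternative measures.** With no effect, the severe share per attack is 20% in every window. The severe-attack rate after dosing is 2 × 0.2 = 0.40 per month. In run-in the entry rule raises it: the mean count given at least 2 is 3.680 × (1 − 0.02523)/0.8819 = 4.067, and 4.067 × 0.2 × 30.4375/56 = 0.44. At a true 1 per month the same steps give 0.31 against 0.20.

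**The case against.** The strongest reply is that the SAP already holds the remedy. The severity-specific rates in 6.4.1 are divided by days, attacks are plotted by severity from run-in onward, and every attack is listed. That stands and lowers the harm, but neither 3.2 nor 6.4.2 makes those rates the severity endpoint, and they do not correct the worst-severity table.

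The study is descriptive and its primary endpoint is safety. That also stands: the risk is a misleading table, not a false test result.

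The full-treatment comparison is inferred from a general display sentence. Correct; it is the likely reading, not an explicit one. The run-in and first-dose tabulations are explicit.

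Three stronger readings are tempting and not supported:

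- *The table must show worsening over treatment.* The directions are tendencies under assumed inputs, and a large effect shows clearly as improvement. At 1 attack per month with a 50% fall, Cohort 1 would show 42% against 45% in run-in, which is not worse.
- *The SAP departs from an attack-level analysis in Protocol 9.6.* That section asks for severity overall and by participant. It names neither attack-level percentages nor a maximum, and a participant-level summary is compatible with it.
- *Cohorts would differ only through their windows.* They receive different regimens; the table mixes the two sources.

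**Conclusion.** The concern holds as a defect of the summary. Worst severity per participant, unadjusted for exposure, cannot separate a change in attack severity from a change in days or attacks observed. With no drug effect it tends to show fewer severe participants in Cohort 3's first-dose period and more over full treatment. A fall in attacks of about half can look like worsening, one of about 70% like little change, and one of 90% still reads as benefit.

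These sizes rest on Poisson attacks, 2 per month and 20% severe, none of which the documents give. The directions are stable over the ranges tried; the sizes are not. The treatment-period figures also depend on reading SAP 6.4 as displaying worst severity for that period. The point is worth correcting before the final analysis, and it does not affect the primary safety endpoint.

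**What to change.** In SAP 3.2 and 6.4.2:

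1. Report, per period, the number and percentage of attacks that are mild, moderate and severe.
2. Name the severity-specific monthly rates in 6.4.1 as the before/after analysis of this endpoint.
3. Keep worst severity only as a listing, or compute it over equal windows, for example the last 28 days of run-in against each 28-day interval after dosing. State the window in the table.
4. Do not set the run-in attack-free category against a post-dose window.

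State two limits beside the results. First, run-in rates are inflated by the entry rule: 0.44 against 0.40 severe attacks per month at a true 2 per month, and 0.31 against 0.20 at 1 per month, an apparent fall of about 35% with no drug effect. Second, attack-free participants contribute no attack-level percentage. With a large effect that matters in cohorts of 4 to 12: at 0.2 attacks per month, exp(−0.2 × 168/30.4375) = 33% would have no attack in 168 days. The rates, which include these participants as zeros, should therefore carry the comparison.

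The cost is SAP wording and one changed table. The data are already collected and the 6.4.1 rates already planned.
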